| Exclusion Criteria | 
 • Women that are pregnant or breast feeding. • Age <18 |

| | |
|----------------------------|--|
| | 
 • Severe kidney dysfunction (GFR <30 mL/min/1.73m²) |
| Treatment Description | ¹⁸ F-DCFPyL whole body PET/CT or PET/MR scan |
| Study Procedures | 
 • ¹⁸F-DCFPyL whole body PET/CT imaging for dosimetry studies; PET/MR scan to achieve other aims • Review of relevant imaging and medical record information |
| Statistical Considerations | 
There are no formal hypothesis tests planned.
 
Our primary goals are to:
 
 1. Record the normal biodistribution and radiodosimetry of PSMA in the body 2. Record the frequency the normal fallopian tubes and ovarian are seen on high resolution MR imaging. 3. Record the distribution of PSMA in cancer tissue 4. Estimate the frequency with which PSMA PET and MR imaging and final IHC staining disagree in their classifications of presence of disease. We will classify each data point as either an agreement or disagreement between imaging findings and IHC staining. The proportion of disagreements across all time points will be estimated with an intercept-only GEE regression model that accounts for correlation among measures from the same patient. This proportion will be reported with a 95% confidence interval. The lower bound of this confidence interval will be used to help us decide whether this approach is worthy of future study. Based on this pilot study we plan to pursue further evaluation in larger more appropriately powered studies if the lower bound of the confidence interval excludes 20%, which is chosen as a guideline to determine whether the method shows promise. |

SCHEMATIC OF STUDY DESIGN

Subject Populations

1.0 PROJECT SUMMARY:

The purpose of our proposal is to use PSMA PET and multi-parametric MR imaging, to detect the presence of gynecological cancer cells in the body. Imaging evaluation would include the appearance of normal ovaries/fallopian tubes, and cancerous tissue on different MR sequences and the distribution of PSMA in normal and pathological tissues on PET images. To determine the accuracy of the PSMA PET imaging localization in malignant tissues, PSMA staining of surgical pathology specimens will be used as the reference standard.

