3.0 STUDY AIMS/STUDY OBJECTIVES

The primary outcome of this research is to evaluate whether a novel imaging approach using PSMA-based ¹⁸F-DCFPyL PET and MR imaging can accurately determine the presence or absence of cancer, the accurate distribution of cancer and the normal biodistribution of PSMA in the abdomen and pelvis on PET imaging. The reference standard for the PSMA localization in cancerous tissue will be histologic and immunologic correlation on the pathologic specimens obtained at the time of standard of care surgical resection for treatment of the gynecological cancer. Specific aims for this research include the following:

1. To establish the biodistribution and radiodosimetry of PSMA-based ¹⁸F-DCFPyL on PET imaging in normal female controls and in females with known or suspected cancer.
2. To determine the sensitivity, specificity, and accuracy values of PSMA-based ¹⁸F-DCFPyL PET and MR imaging in the detection of cancer in women with known or suspected gynecologic malignancy and differentiating cancerous tissue from non-cancerous tissue. The performance of PSMA-based ¹⁸F-DCFPyL PET imaging in the detection and localization of cancerous and non-cancerous tissue will be compared to the final surgical pathology reports and to the histological and immunostaining for PSMA positive cancerous tissue on pathology.
3. To determine the most accurate approach in assessing disease burden and location, assessment of tumor burden on both the PSMA-based ¹⁸F-DCFPyL PET and MR imaging

together, and then each modality separately will be performed and sensitivity, specificity, and accuracy values will be calculated.

4.0 RESEARCH DESIGN AND METHODS:

Subject population

Fifty-two subjects will be enrolled in this research, 12 healthy controls and 40 patients with known or suspected gynecologic cancer. Up to 6 subjects will be used for the dosimetry portion. Eligibility requirements include the following:

Inclusion Criteria for healthy female controls N=12 (includes up to 6 Dosimetry subjects)

1. Women with no suspected gynecological cancer
2. No contraindications for MR or PET imaging
3. Greater than or equal to 18 years of age
4. Scheduled to undergo a hysterectomy and/or salpingo-oophorectomy

Inclusion Criteria for female controls (Dosimetry)

1. Women with or without suspected gynecological cancer
2. No contraindications for MR or PET imaging
3. Greater than or equal to 18 years of age

Inclusion Criteria for gynecologic cancer patients N=40

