5.0 STUDY PROCEDURES

Subjects will be asked to complete a single research visit that will include the administration of a PSMA PET/CT and/or PET/MR exam. Subjects participating in the PET/MR imaging studies will be screened for contraindications to MRI and MR contrast agents using the standard UWCHC MR Safety screening form. A urine pregnancy test will only be done for women with childbearing capacity that are unable to verify their non-pregnancy status by self-report.

Aim 1. Biodistribution and radiodosimetry of PSMA-based ¹⁸F-DCFPyL in normal female controls or cancer patients (Up to 6 subjects for non-dosimetry and 6 subjects for radiodosimetry (dosimetry))

The research visit is estimated to take 2-3 hours, which includes approximately 60-120 minutes of scanning time. Subjects will be asked to fast for 4 to 6 hours prior to the research visit and to stay well hydrated.

The remainder of the time will be preparatory for the scanning. An IV will be placed to allow injection of the PET tracer during the exams.

Dosimetry Subjects: A less than 9 mCi dose of ¹⁸F-DCFPyL radiotracer will be administered by slow IV push after subject has been positioned in the PET/CT scanner. The subject's imaging session will include multi-pass PET scans to allow for normal organ and tumor biodistribution for a total of 5 PET scans from the vertex of skull through mid-thigh. Initial low-dose CT will be followed by 4 PET scans (PET1 through PET4) lasting approximately 60 to 75 minutes (depending on the height of the patient). The subjects will be allowed to leave the table to void between the fourth and fifth (PET5) PET scans. The fifth PET/CT scan (PET5) is obtained with another low-dose CT scan to allow for CT attenuation correction followed by the PET scan starting at approximately 90 minutes after radiotracer administration to last up to approximately 30 minutes (again, depending on the height of the patient). If the PET/CT takes less than 120 minutes, the subject may undergo a PET/MR, as time allows.

Dosimetry Subjects Only - Blood Collection:

- Blood (5mL Purple top at each time point) will be collected at 3 time points, after the completion of the 2nd, 4th and 5th PET passes on the PET dosimetry PET/CT protocol. Blood will be collected for the first 3 subjects and as needed for the remaining 3 subjects.

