- Blood will be counted on a gamma counter after dilution to determine radioactivity on the same day as the scan. After radioactive decay overnight, blood will be disposed of as per routine biohazard.

Non-dosimetry subjects: An IV will be placed to allow injection of the PET tracer, MR gadolinium agent, and glucagon (if needed) during the exams. A less than 9 mCi dose of ¹⁸F-DCFPyL radiotracer will be administered by slow IV push outside the scanner, after which, the subject will be required to sit quietly for 60 minutes to allow for adequate biodistribution of the tracer. The subjects will then be placed in the PET/MR scanner and will remain in the scanner for up to 90 minutes. After which, the whole body (defined in this protocol as base-of-skull to mid-thigh) PET and MR images will be obtained to include images post-intravenous gadolinium contrast. Glucagon (0.5mg-1mg, IV) may be administered by IV prior to the MR imaging if excessive bowel movement is seen on initial images. Glucagon is known to diminish bowel motion and improve MR image quality.

Aims 2 & 3. Sensitivity, specificity, and accuracy values of PSMA-based ¹⁸F-DCFPyL PET and MR imaging and assessment of tumor burden (40 subjects with known or suspected gynecological cancer).

This research visit is estimated to take 2-3 hours. For subjects with gynecologic cancer, the subjects will be in the scanner for up to 90 minutes. The remainder of the time will be preparatory for the scanning. An IV will be placed to allow injection of the PET tracer, MR gadolinium agent, and glucagon (if needed) during the exams. Subjects will be asked to fast for 4 to 6 hours prior to the research visit and to stay well hydrated. There will be a 1-hour uptake period after IV administration of less than 9 mCi of ¹⁸F-DCFPyL radiotracer by slow IV push. After which, the whole body (defined in this protocol as base-of-skull to mid-thigh) PET and MR images will be obtained to include images post-intravenous gadolinium contrast. Glucagon (0.5mg-1mg, IV) may

be administered by IV prior to the MR imaging if excessive bowel movement is seen on initial images. Glucagon is known to diminish bowel motion and improve MR image quality.

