10.0 STATISTICAL CONSIDERATIONS

The goals of this study are to 1) record the normal distribution of PSMA in the body, 2) record the frequency that the normal fallopian tubes and ovarian are seen on high resolution MR imaging, 3) record the distribution of PSMA in cancer tissue, and 4) estimate the sensitivity, specificity, and accuracy of PSMA PET and MR imaging.

12 healthy controls and 40 subjects with known gynecologic cancer will be enrolled in this pilot study. With final IHC staining as the “gold standard” in detection of cancer, we will estimate the sensitivity, specificity, and accuracy of PSMA PET and MR imaging. The sample size was chosen based on logistical and financial considerations. The table below shows the precision with which we will be able to estimate the sensitivity and specificity of PSMA PET and MR imaging.

| Sensitivity/Specificity | Width of 95% CI |
|-------------------------|-----------------|
| 65% | 31.1% |
| 70% | 29.9% |
| 72.5% | 29.3% |
| 75% | 28.5% |
| 77.5% | 27.7% |
| 80% | 26.5% |
| 82.5% | 25.5% |
| 85% | 24.1% |

Based on this pilot study, we plan to pursue further evaluation in larger, more appropriately powered studies if sensitivity and specificity are at least 80%.

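### The section 10 precision table assumes 40 subjects for both sensitivity and specificity; at one result per woman, 52 women cannot supply both

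*Combined protocol and SAP*

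**What the plan says.** Section 10.0 names final IHC staining as the reference standard and describes enrolment as follows: "12 healthy controls and 40 subjects with known gynecologic cancer will be enrolled in this pilot study". On the basis for that number it says "The sample size was chosen based on logistical and financial considerations". It then presents the table with the words "The table below shows the precision with which we will be able to estimate the sensitivity and specificity of PSMA PET and MR imaging". The table has one width column, headed for sensitivity and specificity together, running from 31.1 points at 65% to 24.1 points at 85%. It states no n, no interval method and no unit of analysis. The sentence after the table sets the continuation rule: "we plan to pursue further evaluation in larger, more appropriately powered studies if sensitivity and specificity are at least 80" per cent.

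Other sections bear on the denominators:

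- Section 5.0 assigns the accuracy aims (Aims 2 and 3) to the cancer group only, and describes that group more broadly than section 10 does: "assessment of tumor burden (40 subjects with known or suspected gynecological cancer".
- Section 4.0 heads the control criteria "Inclusion Criteria for healthy female controls N=12 (includes up to 6 Dosimetry subjects". The separate dosimetry criteria admit women with or without suspected cancer and do not list surgery, although the synopsis places these subjects among controls having surgery.
- Dosimetry subjects have PET/CT. For PET/MR, section 5.0 says "If the PET/CT takes less than 120 minutes, the subject may undergo a PET/MR, as time allows".
- The synopsis plans "an intercept-only GEE regression model that accounts for correlation among measures from the same patient", but only for the proportion of imaging and staining disagreements.

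**The concern.** Sensitivity and specificity have different denominators, and at patient level the two must add up to no more than the number of women enrolled. One width column applied to both measures implies the same n for each. If that n is 40, the table assumes 80 women.

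Because the sample size was not derived statistically, this table is the only place where the plan tells readers how precisely sensitivity and specificity will be known. If it is too favourable for one measure, a result that meets the 80% rule on a small number of negatives will look firmer than it is.

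**Working it through.** **Inputs.** Section 10.0: 40 cancer subjects, 12 controls, eight printed widths, 95% confidence. Section 4.0: 52 women in total, up to 6 dosimetry subjects among the 12 controls.

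**Formula.** For x correct results out of n, the exact limits are: lower = Beta quantile 0.025 with parameters (x, n−x+1); upper = Beta quantile 0.975 with parameters (x+1, n−x). Width = upper − lower. Where 0.8n is not a whole number, x = 0.8n is put into the same quantiles.

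**Step 1: reproduce the table, then set n=12 beside it.** With n=40 and limits rounded to 0.1 before subtraction, every row matches.

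| Value | x of 40 | Limits at n=40 | Width | Printed | Width at n=12 | n=12 ÷ printed |
|---|---|---|---|---|---|---|
| 65% | 26 | 48.3 to 79.4 | 31.1 | 31.1 | 55.7 | 1.79 |
| 70% | 28 | 53.5 to 83.4 | 29.9 | 29.9 | 54.0 | 1.81 |
| 72.5% | 29 | 56.1 to 85.4 | 29.3 | 29.3 | 52.9 | 1.81 |
| 75% | 30 | 58.8 to 87.3 | 28.5 | 28.5 | 51.7 | 1.81 |
| 77.5% | 31 | 61.5 to 89.2 | 27.7 | 27.7 | 50.3 | 1.82 |
| 80% | 32 | 64.4 to 90.9 | 26.5 | 26.5 | 48.7 | 1.84 |
| 82.5% | 33 | 67.2 to 92.7 | 25.5 | 25.5 | 47.0 | 1.84 |
| 85% | 34 | 70.2 to 94.3 | 24.1 | 24.1 | 45.0 | 1.87 |

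The unrounded width at 80% is 26.6. At n=39 or n=41 the same method misses most rows by 0.3 to 0.5 points. At 80% with n=40, Wald (24.8) and Wilson (24.3) do not match.

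**Step 2: count the women.** 40 positives + 40 negatives = 80, against 52 planned. This does not depend on the interval formula: the best-fitting n is 33 under Wilson, 35 under Wald and 42 under Wald with continuity correction, and twice the smallest of these is 66.

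**Step 3: widths at 80% for the possible splits of 52.** The documents give no expected share of reference-positives among the 40, so the share is an assumption. All 12 controls are taken as reference-negative and pooled with any negatives among the 40.

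| Assumed share of the 40 positive | n positive / negative | Sensitivity width | Specificity width |
|---|---|---|---|
| 100% | 40 / 12 | 26.6 | 48.7 |
| 90% | 36 / 16 | 28.1 | 42.4 |
| 80% | 32 / 20 | 29.8 | 37.9 |
| 70% | 28 / 24 | 32.0 | 34.6 |
| 65% (equal split) | 26 / 26 | 33.2 | 33.2 |
| 50% | 20 / 32 | 37.9 | 29.8 |

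No split gives 26.5 for both. The smallest achievable value of the larger width is 33.2 (33.2 ÷ 26.5 = 1.25).

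A specificity of exactly 80% cannot occur on 12 women. The neighbouring results are 9/12 (42.8% to 94.5%, width 51.7) and 10/12 (51.6% to 97.9%, width 46.3).

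**Step 4: dosimetry subjects.** If 6 of the 12 controls contribute no PET/MR or no tissue, and all 40 patients are positive, n=6 and the width is 66.3 (66.3 ÷ 26.5 = 2.5). This is the worst case.

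**Step 5: the 80% rule, as an illustration.** Assume true sensitivity 85% and true specificity 70%; neither figure is in the documents.

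- P(at least 32 of 40 at 0.85) = 86.5%.
- P(at least 32 of 40 at 0.70) = 11.1%; the product is 9.6%.
- P(at least 10 of 12 at 0.70) = 25.3%; the product is 21.9%.

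So the chance of meeting both parts of the rule, when specificity is really 70%, is 21.9% with 12 negatives against 9.6% with the 40 that the table implies.

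**Step 6: site-level reading.** With k women, m negative sites each and within-woman correlation ρ, effective n = km ÷ (1 + (m−1)ρ). Taking ρ = 0.5 and m = 2 as assumptions, 40 women give 80 ÷ 1.5 = 53 and 20 women give 40 ÷ 1.5 = 27. An effective n of 40 may or may not be reached.

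**The case against.** The strongest reply is that one result per woman is not the plan's unit. The aims speak of telling cancerous from non-cancerous tissue and of locating disease, section 5.0 selects named sites for staining, and the synopsis allows for several measures per patient. If each of the 40 women gave exactly one cancerous and one benign site, both measures would have n=40 with no clustering within either. That reading would make the table correct, but the documents nowhere state it, and it requires every one of the 40 to have a reference-positive site. The synopsis GEE model is tied to the disagreement proportion, not to this table. What stands is that a site-level analysis could supply n=40 for both, so the finding is conditional on the unit.

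A second reply is that section 5.0 gives the accuracy aims to the 40 patients alone, so 12 is not the right denominator for specificity. That makes the shortfall worse: within 40 women the best equal split is 20/20, with 37.9 points for each measure.

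Third, the 12 are not certain negatives, because dosimetry subjects may have suspected cancer. This is fair, and it is one more reason to state expected counts.

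Finally, the sample size is logistical, no formal tests are planned and the 80% rule uses point estimates, so no calculation uses the widths. That limits the consequence; it does not make the stated precision right. The table is what a reader will use to judge how far to trust a result that meets the rule.

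**Conclusion.** The concern holds. At one result per woman, the table is too favourable for at least one of the two measures under every split of the 52 women.

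On section 10's own description, and assuming the 40 are all reference-positive and the 12 all reference-negative, sensitivity keeps its stated precision and specificity does not: 48.7 points at 80% against 26.5, and 1.79 to 1.87 times the printed width across the rows. If 50% to 90% of the 40 are positive and the rest are pooled with the controls, specificity is 1.13 to 1.60 times and sensitivity 1.06 to 1.43 times the stated width.

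The existence of the shortfall rests only on the patient as unit. Its size rests on the assumed split and on whether dosimetry subjects contribute. At site level the table may or may not hold, and section 10 does not give what is needed to tell. The point should be fixed; it does not invalidate the trial.

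**What to change.** In section 10.0:

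- State the unit of analysis and that the intervals are exact.
- Replace the single column with separate sensitivity and specificity columns, each with its own expected number of reference-positive or reference-negative units under the IHC standard.
- If the patient is the unit, print 48.7 points for specificity at 80% with n=12, and a range for an assumed share of reference-negative patients (for example 42.4 at n=16 and 34.6 at n=24), with the matching sensitivity widths (28.1 at n=36 and 32.0 at n=28).
- State whether the controls enter the accuracy analysis at all, given that section 5.0 assigns it to the 40 patients, and whether dosimetry subjects count toward PET/MR specificity.
- Describe the 40 the same way throughout, as known or as known or suspected cancer.
- Note beside the 80% rule how imprecise the specificity criterion is at this n (10/12: 51.6% to 97.9%).
- If sites are the unit, give the expected number of negative sites per woman and widths that allow for within-woman correlation.

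The cost is restated figures and definitions, with no extra patients. The stated precision becomes less favourable, and the plan must commit to an assumed reference-positive share.

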11.0 DRUG FORMULATION AND PROCUREMENT

Investigation Product

The investigational product will be obtained from the University of Wisconsin Radiopharmaceutical Production Facility (RPF). The RPF is located in the Wisconsin Institute for Medical Research Building. The FDA IND for this protocol will be cross-filed with the current Johns Hopkins University IND for ¹⁸F-DCFPyL, IND # 121064 to reference the Pharmacology and Toxicology, dosimetry, and Previous Human Experience sections of that IND.

Common Name: DCFPyL

[figure not shown]
Chemical Names: 2-(3-{1-Carboxy-5-[(6-fluoro-pyridine-3-carbonyl)-amino]-pentyl}-ureido)-pentanedioic acid

Characteristics: hygroscopic white powder

Chemical Formula: C₁₈H₂₃FN₄O₈

C.A.S. Number: 1423758-00-2

Structure:

Molecular Weight: 442.40

Solubility: Soluble in DMSO, methanol, 1:1 acetonitrile:water

¹⁸F-DCFPyL is eluted with 1 mL of ethanol followed by 10 mL of 0.9% sodium chloride, via a sterilizing 0.22 μ filter into a sterile vial containing 4 mL 0.9% sodium chloride. Test radiopharmaceutical will be administered intravenously via slow I.V. push. The maximum mass dose of the ligand corresponding to the <9 mCi dose of ¹⁸F-DCFPyL will be less than 3.98 μ g per administration, although the actual dose will be significantly less depending on the specific activity achieved during each radiosynthesis run. The lowest limit for specific-activity (SA) we will use at the time of injection is 1000 mCi/ μ mole, although the validation and phase I study radiosynthesis SA was significantly higher than 1000 mCi/ μ mole.

Preclinical Toxicology

A toxicity report “14-Day Study to Determine Toxicity of DCFPyL from a Single IV Dose in Sprague Dawley Rats” was prepared by SoBran Inc. (Study No. SB-MP-001). The following summary is taken from that report.

The purpose of this study was to evaluate the toxicity of DCFPyL three and fifteen days following a single intravenous dose in rats. This study consisted of two test article treatment groups of ten male and female Sprague-Dawley rats per group dosed with DCFPyL at 0.1 and 0.5 mg/kg. An additional group of ten males and ten females received the vehicle, 5% Dextrose, and served as the control. All rats received a dose volume of 5 mL/kg. The rats were dosed intravenously once on Study Day 1. Five male and five female rats from each group were bled on Study Day 3 and the remaining rats were bled on Study Day 15. All animals were euthanized and necropsied following blood collection. Parameters evaluated for test article effect included survival, clinical observations, body weight, body weight gain, clinical pathology, gross pathology, organ weights, and microscopic pathology.

All rats survived to the scheduled termination and remained bright, alert and responsive during the study. No abnormal findings were indicated during cageside or hands-on observations. One female rat treated with the vehicle control and one female rat treated with 0.1 mg/kg DCFPyL lost weight between Days 8 and 15. All rats treated with 5% Dextrose or DCFPyL gained weight during the course of the study. There were no treatment related changes seen in the hematology, coagulation, or clinical chemistry data. Organ weights showed some variance but microscopic findings in the Day 3 and Day 15 rats were considered incidental and not directly related to the test article. Under the conditions of this study, there were no treatment related findings in Sprague Dawley rats three or fifteen days after a single intravenous dose of DCFPyL at 0.1 mg/kg and 0.5 mg/kg.

| Organ | 30 min | 60 min | 120 min | 240 min |
|-----------------|-------------|-------------|-------------|-------------|
| Blood | 1.53 ± 0.19 | 0.24 ± 0.05 | 0.43 ± 0.37 | 0.03 ± 0.01 |
| Heart | 0.68 ± 0.07 | 0.20 ± 0.11 | 0.06 ± 0.01 | 0.02 ± 0.00 |
| Lung | 1.91 ± 0.47 | 0.55 ± 0.17 | 0.18 ± 0.02 | 0.06 ± 0.00 |
| Liver | 3.88 ± 0.74 | 2.87 ± 0.92 | 2.14 ± 0.11 | 1.80 ± 0.39 |
| Stomach | 1.50 ± 1.12 | 0.35 ± 0.34 | 0.08 ± 0.03 | 0.02 ± 0.00 |
| Pancreas | 1.02 ± 0.53 | 0.26 ± 0.13 | 0.08 ± 0.00 | 0.03 ± 0.01 |
| Spleen | 7.59 ± 3.56 | 2.70 ± 1.28 | 0.69 ± 0.11 | 0.23 ± 0.09 |
| Kidney | 74.1 ± 6.6 | 42.3 ± 19.0 | 15.7 ± 3.3 | 7.42 ± 0.89 |
| Muscle | 0.39 ± 0.05 | 0.61 ± 0.92 | 0.04 ± 0.00 | 0.05 ± 0.05 |
| Bone | 0.82 ± 0.16 | 0.42 ± 0.15 | 0.33 ± 0.08 | 0.43 ± 0.06 |
| sm. Intest | 0.79 ± 0.11 | 0.31 ± 0.12 | 0.11 ± 0.07 | 0.05 ± 0.01 |
| Irg. Intest | 0.73 ± 0.04 | 0.40 ± 0.17 | 0.12 ± 0.05 | 0.06 ± 0.01 |
| Bladder (empty) | 18.6 ± 18.1 | 9.88 ± 4.92 | 6.44 ± 4.42 | 1.54 ± 1.79 |
| PSMA+ PIP | 46.7 ± 5.8 | 44.2 ± 9.7 | 39.4 ± 5.4 | 36.6 ± 4.3 |
| PSMA- flu | 1.17 ± 0.41 | 0.36 ± 0.14 | 0.11 ± 0.02 | 0.03 ± 0.01 |
| PIP/flu | 40 | 123 | 358 | 1220 |

^aValues are in% ID/g SD; n = 4.

¹⁸F-DCFPyL was assessed for its ex-vivo pharmacokinetics in non-obese diabetic severe-combined immunodeficient (NOD-SCID) mice bearing both PSMA positive PC3-PIP and PSMA negative PC3-flu xenografts. Table below shows the percent injected dose per gram of tissue (%ID/g) of ¹⁸F-DCFPyL activity in selected organs.

¹⁸F-DCFPyL PSMA-dependent uptake within PSMA positive PC3 PIP xenografts, reaching a value of $46.7 \pm 5.8\%$ ID/g at 30 minutes post-injection (p.i.), which decreased by only about 10% over the ensuing 4 hours. At 60 minutes p.i. the kidney, liver, and spleen displayed the highest uptake. By that time, the urinary bladder also showed relatively high uptake. However, that uptake includes excretion at all-time points. Rapid clearance from the kidneys was shown, decreasing from $74.1 \pm 6.6\%$ ID/g at 30 minutes to $7.4 \pm 0.9\%$ ID/g at 4 hours. The relatively high values noted in kidney are partially due to high expression of PSMA within proximal renal tubules. The ratio of uptake within PSMA positive PIP to PSMA negative flu tumors ranged from 40:1 to more than 1,000:1 over the 4-hour time period of the study. A possible explanation for that increased tumor uptake of radiochemical over time could be due to ligand-mediated PSMA internalization within tumor cells. Less retention in kidney relative to tumor over time could be due to a lower degree of internalization in this (normal) tissue and/or different metabolism of ¹⁸F-DCFPyL, which does not promote retention of radiochemical in kidney. Relatively low bone uptake (<1% ID/g at all-time points) suggests little metabolic defluorination of ¹⁸F-DCFPyL. The total effective dose for 333 MBq (9 mCi) of ¹⁸F-DCFPyL was calculated to be 5.93 mGy (0.593 rem) based on animal models.

Initial Phase I Study Adverse Events:

An initial phase I study of the biodistribution and dosimetry of ¹⁸F-DCFPyL found that in nine patients there were no severe adverse events. One patient reported two adverse events that were classified as unlikely to be attributable to the radiotracer (mild headache and mild nose bleed, both of which resolved without treatment and were considered Grade I by the National Cancer Institute Common Terminology Criteria for Adverse Events (NCI CTCAE) Version 4.0). Another participant experienced a decrease in platelet count on routine assessment during the post-imaging follow up which, at the time of publication, had not resolved but which was attributed to the participant starting treatment for prostate cancer. This was also a NCI CTCAE Grade I adverse event. There were no radiotracer-related adverse events with monitored heart rate or blood pressure.

Human dosimetry: 18F-DCFPyL human dosimetry reported in Risks/Benefits section.

